
Ohio State Medicaid Policy Change

Prior to July 2013, children with disabilities were eligible for traditional, fee-for-service Medicaid. In July 2013, all ABD children in Ohio were required to enroll in managed care. The policy change effectively moved approximately 8,000 Medicaid-eligible ABD children into the Partners for Kids (PFK) ACO. Partners for Kids (PFK) is owned by Nationwide Children’s Hospital, and assumes responsibility for approximately 300,000 Medicaid children in central and southeastern Ohio (34 of 88 counties).

Study Population

Defining the Study Population:

[figure not shown]

Figure 1: SSI vs. ABD in Ohio

The Social Security Administration (SSA) considers a child under age 18 disabled if the child 1) is not working at a job considered to be substantial work; 2) has a physical or mental condition that results in “marked and severe functional limitations”; and 3) the condition(s) has lasted or is expected to last at least 1 year or expected to result in death.[32] In most states, children who are Medicaid-eligible under the Aged/Blind/Disabled (ABD) category are the same children who qualify for Supplemental Security Income (SSI) under the SSA’s disabled definition. In Ohio and other “209b” states, the eligibility criteria for

Medicaid are more restrictive. In these states income-eligibility level for Medicaid may be set lower than that required for SSI eligibility, although it also allows for “spend down” to Medicaid monthly income eligibility by deducting medical expenses.[33] The result is that most, but not all, SSI children in Ohio also qualify for Medicaid under Ohio’s ABD definition (**Figure 1**).

Because Medicaid eligibility is not automatic for all SSI children in Ohio, we refer to the disabled children population in this research proposal as “ABD children.”

Study Justification

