Sub-aim 1a: Interviews with ACO Stakeholders: We will conduct key informant interviews with ACO stakeholders in order to identify care coordination strategies for ABD children before and after the policy change. We will sample purposively from four groups: ACO leaders, care coordinators, clinicians, and payor representatives. Each group will provide a different perspective on coordination objectives and strategies. ACO leaders can speak to the goals of the ACO. Care coordinators and clinicians can speak to the day-to-day practices of coordinating care. Payor representatives can speak to the motivations to delegate care coordination to the ACO and ongoing efforts to monitor this delegation. We will work with the ACO to identify and select key informants from each of the four stakeholder groups based on their knowledge about and experience with care coordination related decisions and practices for ABD children. At least two researchers will attend each in-person interview. The role of the researchers will be to prompt for additional details and to take notes. Each interview will last about one hour and will be digitally recorded and subsequently transcribed.

Sub-aim 1b: Focus groups with patients and caregivers and interviews with caregivers: We will conduct focus groups with patients and caregivers and interviews with caregivers in order to obtain their perceptions of the relative quality, value and experience of care and care

coordination under the two systems. We will recruit participants through the following means: 1) distribution of flyers throughout ACO provider sites and ACO care coordinators; 2) recruitment email sent through Patient Advisory Panel and Voice's For Ohio's Children listserv; and 3) snowball-sampling approaches to identify additional participants based on referrals from other participants. To be eligible to participate, the child (as the participant or of the caregiver) must:

1. Have resided continuously in the region served by the ACO, have been continuously enrolled in Medicaid, and have had ABD status since at least one year before the policy change;
2. Be no more than 18 years of age at the time of data collection; and
3. Have been, at the time of the policy change, at least 14 years of age for patient focus groups or 2 years of age for caregiver focus groups and interviews.

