These criteria ensure that participants will have had sufficient, relevant experience under both systems to be able to compare them. All recruitment materials will be developed by the research team in consultation with Patient Advisory Panel members and will be subjected to review by the Institutional Review Boards at UNC-Chapel Hill, The Ohio State University, and Nationwide Children's Hospital.

We will conduct a total of ten 1.5-hour focus groups, each with roughly 10-12 participants. Under guidance from members of our Patient Advisory Panel, we have developed a strategy that samples based on broad categories of disability and geographic location (**Table 1**). This approach will allow us to maximize the overall variation in our sample through inter-group diversity, while simultaneously ensuring focused, productive discussions within each group through intra-group similarity. While caregivers of ABD children are often the primary point of contact for coordination activities, we recognize that individuals with disabilities will have unique perspectives. Two focus groups with disabled teenagers will therefore be conducted to ensure these perspectives are incorporated. All focus group discussions will be guided by questions we have developed with input from our Patient Advisory Panel Members (**Appendix C**). One researcher will moderate these discussions, ensuring all participants have opportunities to share their thoughts, including those that differ from the majority. A second researcher will take notes. Focus group discussions will be recorded and transcribed.

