relevant to the coordination of care for children with disabilities. For interviews with ACO stakeholders, we will sample purposively from four groups: ACO leaders, care coordinators, clinicians, and payor representatives. Each group will provide a different perspective on coordination objectives and strategies. For focus groups with youths and caregivers and interviews with caregivers, we will sample based on broad categories of condition and geographic location (rural v. urban). This approach will allow us to maximize the overall variation in our sample through inter-group diversity, while simultaneously ensuring focused, productive discussions within each group through intra-group similarity. Finally, for the interviews with Caregivers, we intend to select 30 parents, as this number provides a large enough sample to gather a rich mix of different stories and experiences in rural and urban settings and from parents of children with different types of disabilities.

To be eligible to participate in ACO stakeholder interviews, participants must be involved with the ACO as either an ACO leader, a care coordinator or clinician, or as a representative of a payor organization (i.e., insurer). To be eligible to participate in focus groups or caregiver interviews, the child (as the participant or of the caregiver) must:

1. have resided continuously in the region served by the ACO, have been continuously enrolled in Medicaid, and have had ABD status (i.e., Medicaid disability status) since at least one year before the policy change;
2. be no more than 18 years of age at the time of data collection; and
3. have been, at the time of the policy change, at least 14 years of age for youth focus groups or 2 years of age for caregiver focus groups and interviews.

Children under the age of 15 will be excluded on the grounds that they may not be able to recall with sufficient detail their experiences under the previous Fee-for-service system. These criteria ensure that participants will have had sufficient, relevant experience under both systems to be able to compare them.

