 - CSRL will mail the follow-up letter to non-opt-out families with a web link and code. Participants will have one month to answer. After the month, CSRL will discontinue access to the web and then will know which part of the sample remaining to be called.
- Eligibility/Survey Administration
 - NCH will provide a summary of demographic data on opt-outs.
 - Families with more than 2 eligible patients – ask about the patient (i.e. child) for whom the interviewer is calling only.
 - Interviewer will ascertain which caregiver is the one who obtains health care/ the most involved in going to health care visits with the child and interview this person.
 - At end of survey, interviewer will confirm to whom the check should be mailed and confirm mailing address – participant can choose any person to send check to.
 - We will add 'Yes I agree, No I don't agree' for consent box at the end of survey – this will serve as documentation that interviewer obtained verbal consent.
- Reporting
 - CSRL will provide weekly reports on calls that will include such information as: bad numbers, number called, number ineligible, those we haven't screened, screened but declined, and completed, and medical record consents. May also include how long the interview has taken and profiling.

Timeframe

March 1 UNC provide CSRL with all IRB-approved materials, including consent

materials, screener, and the survey in both English and Spanish.

March 27	CSRL send web-based survey link for pilot testing with the patient advisory panel.
March 27- April 5	Patient advisory panel members pilot the web-based survey.
April 6	Quarterly Advisory Panel Meeting – investigators solicit PAP input including such things as need for more instructions, navigation issues, using the interface (do links work, etc.), is survey user-friendly.
April 10	UNC provide feedback about the web-based survey to CSRL
May 1	PFK mail out opt-out letters.
May 31	Preliminary demographics due to PCORI (prepared by NCH).
June 9	End of 40-day period.
June 23	NCH send eligible sample to CSRL.
July 1	Begin web survey. CSRL send follow-up letters to eligible sample with code and web address.
July 31	End date for web survey.
August 1	Begin telephone survey.
October 31	End date for telephone survey.
Nov 30	CSRL send final dataset to UNC.

Medical Record Review

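### In the Sub-aim 1b caregiver groups and interviews, eligibility rests on the child's history alone, so it does not ensure that the caregiver knew both systems

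*Combined protocol and SAP*

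**What the plan says.** The criteria appear twice. Under Aim 1, Data Collection, Sub-aim 1b, they open with "To be eligible to participate, the child (as the participant or of the caregiver) must". Under Procedures, Aim 1, they open with "To be eligible to participate in focus groups or caregiver interviews, the child (as the participant or of the caregiver) must". Three conditions follow in both places:

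- The child has lived in the ACO region and been enrolled in Medicaid without a break, and must "have had ABD status since at least one year before the policy change".
- The child must "Be no more than 18 years of age at the time of data collection".
- At the policy change, the child must have been "at least 14 years of age for patient focus groups or 2 years of age for caregiver focus groups and interviews".

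Procedures adds one exclusion on grounds of recall, for children under 15. Both sections then draw the same conclusion: "These criteria ensure that participants will have had sufficient, relevant experience under both systems to be able to compare them".

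The policy change is dated under Ohio State Medicaid Policy Change: "In July 2013, all ABD children in Ohio were required to enroll in managed care".

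Table 1 plans eight caregiver focus groups, two teenager groups and 30 caregiver interviews. The step lists for caregiver focus groups and caregiver interviews include an eligibility check by telephone. They do not say what is asked, and the form name is left blank.

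**The concern.** In a teenager group the child is the participant, so conditions on the child test the right person. In a caregiver group or interview the participant is an adult whose own history with the child's care is never tested. A foster, kinship, adoptive or step-parent, or a parent who took over later, can satisfy the rule through the child without having dealt with the child's care under fee-for-service.

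This matters because of how the material is used. The Aim 1 Data Analysis section draws on all the qualitative data to set out the advantages and disadvantages of each model. The mixed-methods section then merges these findings with the claims results and treats agreement between the two as stronger support. Statements about fee-for-service from someone who did not see it with this child are second-hand, and nothing in the plan would mark them as such.

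**Working it through.** The plan offers no figure to reproduce here. The check sets each criterion against a test case and then counts the people the rule governs.

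**Test case.** A caregiver starts in 2014. The child has had continuous regional residence, Medicaid enrolment and disability status since before July 2012 (one year before July 2013), was at least 2 in July 2013, and is 18 or younger at data collection.

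| Criterion | Whose history is tested | Result |
|---|---|---|
| Residence, Medicaid and disability status since a year before the change | Child | Met |
| Upper age at data collection | Child | Met |
| Minimum age of 2 at the change | Child | Met |
| Caregiver's involvement before July 2013 | Not tested | – |

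The caregiver is eligible, with no fee-for-service experience with that child.

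**Is a caregiver condition stated elsewhere?**

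- The under-15 exclusion in Procedures concerns the young person's recall. Caregivers have no counterpart.
- Recruitment is by flyers, care coordinators, an email list and referral by other participants. None of these routes tests how long someone has been a caregiver.
- The Aim 1 analysis text acknowledges imperfect recall. Having no exposure to recall is a different problem.

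**What the criteria were meant to do.** A child who was 2 at the change will not be asked to compare two payment systems. In caregiver sessions, the conditions on the period before the change serve the stated purpose only as a stand-in for the caregiver's experience. That stand-in fails whenever the caregiver changed.

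**How many people the rule governs.**

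- Caregiver focus groups: 8 × 10 = 80 to 8 × 12 = 96. At the Table 1 average of 110 / 10 = 11 per group, 8 × 11 = 88.
- Caregiver interviews: 30.
- Together: 80 + 30 = 110 to 96 + 30 = 126, or 88 + 30 = 118 at the average.
- All Sub-aim 1b participants: 110 + 30 = 140.

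These are the people to whom the untested condition applies. They are not a count of people who lack the experience.

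**The case against.** The strongest reply concerns the interviews. The Interviews with Caregivers text seeks accounts of both models and recruits people whose experiences make them useful for comparing the two. That addresses the same risk. It is a sampling intention rather than a criterion, and it is not stated for the focus groups, so it narrows the point without removing it. The gap is mainly in the eight groups.

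A second reply is that the screening form and the focus group guide are not in the supplied text, and that follow-up questions in a semi-structured session may bring a short tenure to light. Both are possible. Neither rescues the written claim, which rests on the listed criteria.

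Third, this is a purposive qualitative component and no quantitative estimate depends on it. That is correct, and it limits the weight of the point.

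Some stronger readings are tempting but are not supported:

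- *All of Aim 1 is affected.* It is not. Stakeholders are chosen by role, and in the teenager groups the criteria test the participant.
- *Aim 2 handles this properly and Aim 1 does not.* The survey procedure says "Interviewer will ascertain which caregiver is the one who obtains health care", but this identifies the caregiver most involved now, not since when. The 2014 caregiver would pass it too.
- *The fee-for-service side of the comparison is biased.* The documents show neither that any participant is affected nor which way an effect would run.
- *The number affected can be estimated.* Any turnover rate would be an outside assumption. A new main caregiver may also have been in the household earlier and seen care under fee-for-service.

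**Conclusion.** The point holds for caregiver participants in Sub-aim 1b: fully for the eight focus groups (about 80 to 96 people), and less so for the 30 interviews. The criteria admit a caregiver with no fee-for-service experience with the child, so the statement that they ensure experience of both systems is not true of caregivers. This follows from the text and needs no assumption about how often caregivers change. How many participants would be affected, and in which direction their accounts would pull the findings, is unknown. The consequence is a weaker basis for the qualitative before/after comparison. No sample size, power or claims-based result changes. It is worth correcting because the repair is small and the plan itself relies on the property that is missing.

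**What to change.** 1. In both places where the Sub-aim 1b criteria are listed (Data Collection, and Procedures for Aim 1), add a condition for caregiver groups and interviews: the participating caregiver must have been involved in arranging or attending the child's health care before the July 2013 policy change as well as after it.
2. Ask this as one question, with the start date of involvement, at the existing eligibility check in the caregiver focus group and caregiver interview steps. Record tenure with the transcript.
3. If a caregiver without involvement before the change has already been enrolled, use that person's data for the ACO period only and leave them out of before/after statements.

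The condition should not demand continuous main-caregiver status from a full year before the change. That would turn away people with real but shorter or shared fee-for-service experience, and would work against the stated aim of a diverse sample.

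The cost is one sentence of protocol text and one screening question. Some volunteers may have to be replaced, and the documents give no basis for saying how many. The planned group sizes and the 30 interviews are unchanged.

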The proposed study uses a recent policy change in Ohio as a natural experiment to assess outcomes and experiences of ABD children and their caregivers in an ACO model of care compared to their previous outcomes and experiences in a traditional fee-for-service model. Prior to the policy change, nearly all of the 38,000 Medicaid-eligible ABD children in Ohio were enrolled in a traditional fee-for-service plan. After the policy change went into effect in July 2013, all ABD children were required to enroll in managed care. In central and southeastern Ohio, the policy change effectively moved approximately 8,000 Medicaid-eligible ABD children into the *Partners for Kids* (PFK) ACO.

PFK is the nation's largest and oldest pediatric ACO focused solely on Medicaid-enrolled children. Established in 1994, PFK is a not-for-profit physician hospital organization jointly owned by Nationwide Children's Hospital in Columbus, Ohio and by a 750+ physician group comprised of primary care physicians, pediatricians, and specialists. In 2013, Nationwide Children's Hospital served 1,000,000 patient visits, 21,000 annual inpatient admissions and 68 facilities including outpatient centers, urgent care, research, and primary care and specialty physician offices. As an ACO, PFK currently provides both primary and specialty care to more than 300,000 Medicaid children enrolled in one of 5 Medicaid managed care plans operating in 34 counties (out of 88 total counties in Ohio) stretching from urban Columbus to rural Appalachia.

Research Questions

The proposed study will address the following research questions:

- 1) Can an ACO implement a system of care coordination that improves upon what children with disabilities and families received before becoming part of an ACO?; and
- 2) What effects do these activities have on health care and outcomes?

Hypothesis

Children with disabilities will have improved outcomes and experiences after becoming part of an ACO compared to their prior outcomes and experiences in a traditional fee-for-service model.

Study Aims

Aim 1

Use qualitative methods to identify stakeholder perspectives on care coordination before and after the transition from fee-for-service to the ACO model of care for children with disabilities.

Aim 2

Implement a novel caregiver and medical record abstraction tool designed to assess care coordination for children with special health care needs to evaluate the quality of care coordination provided by the ACO.

Aim 3

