We will use the same methods for analyzing all of the data gathered for Aim 1. Following standard qualitative coding techniques, we will code data segments within transcripts using labels that capture ideas contained in the data.[37,38] Related codes will then be grouped into themes that highlight common perceptions, ideas, or experiences across informants. We will follow an iterative approach to analysis that involves ongoing cycles of reading and coding transcripts, reviewing the literature, and discussing findings among the research team to identify themes. Throughout the process we will use the constant comparative method comparing data with data, data with codes, codes with codes, and codes with themes, in order to construct a detailed framework of perceptions regarding the effectiveness of care coordination strategies. [39,40] The research team will use the Atlas.ti software package (version 9.0) to facilitate the managing and coding of qualitative data. Our study investigators have used this approach in several previous studies.[41–44] Using all of the qualitative data (i.e., focus groups and ACO stakeholder and caregiver interviews), we will identify the advantages and disadvantages of each model and the situations under which each model is likely to be more or less effective based on patient and stakeholder perceptions of outcomes. We acknowledge that the retrospective nature of Aim 1 may affect recall. However, our intent will be to understand the perceptions of various stakeholder groups regarding care coordination under the two models, as well as, their experiences before, during and after the policy change. Under this aim we will investigate the extent to which participants perceive care coordination to have changed and their own assessments of the effects of any such changes.

Aim 2

In Aim 2, we will add to our qualitative assessment of care coordination and perceived changes in care coordination, using a newly developed quantitative care coordination measurement tool. This tool will measure experiences with and documentation of care coordination in the first year after the transition to the ACO. Data from this measurement will be used to describe the extent of care coordination, to assess whether measured care coordination is consistent with expectations identified in Aim 1, and to measure the relationships between care coordination and patient-centered utilization outcomes.

Caregiver Survey

Participants & Sample Size

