We will first calculate performance on each of the 31 care coordination measures using data from the FECC and the care coordination medical record review. We will stratify indicator performance by age group, urban/rural residence, and disabling diagnosis (physical vs. mental diagnosis). Where appropriate, performance in our sample will be compared with pilot data collected by COE4CCN. We will then link data from the FECC, the medical record review, and the PFK claims data, at the individual level, to assess the relationship between receipt of care coordination elements and selected outcomes. For example, this linked database will allow us to test the relationship between receipt of a useful and understandable discharge summary following an inpatient stay and 30 day readmission or the relationship between regular communication with a designated care coordinator and use of the emergency department. Specific quality/outcomes measures to be studied will be drawn from claims and EMR-based CHIPRA and HEDIS measures with input from our advisory panel. We expect limited missing data in the survey and medical record data due to our data collection methods. Missing data from the survey and the medical record review will be handled using the “available case

analysis approach” in which all cases with complete data for a selected analysis are included in that analysis.

The proposed analysis in Aim 2 will allow us to 1) quantitatively assess the quality and completeness of care coordination offered to ABD children upon roll-in to the ACO; 2) determine whether that quality and completeness is consistent across selected subpopulations; and 3) understand the relationships between elements of care coordination and patient-centered measures of quality and outcomes.

Aim 3

In Aim 3, we will compare quality, utilization, and other patient-centered outcomes for ABD children before and after joining an ACO in Ohio using claims, survey and medical record data. Our comparative analysis includes both quantitative and qualitative measures identified through Aims 1 and 2. In addition, we will triangulate findings from our quantitative, qualitative and care coordination assessment analyses to provide a robust and multi-faceted analysis of the comparative effectiveness of care coordination under a fee-for-service system compared to an ACO model for children with disabilities.

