Administrative data-derived measures include items such as continuity of care, use of the emergency department, hospitalizations, and access to primary and specialty care, timely follow-up after initial prescriptions of ADHD medications or after psychiatric hospitalization.[45,46] We will incorporate recent methodological advances in operationalizing these measures from administrative data.[47] All study measures will be reviewed with our Patient Advisory Panel in order to prioritize the measures determined to be of greatest importance to our patient population. The Patient Advisory Panel may also propose and prioritize additional patient-centered outcome measures during the first two years of the project.

Key treatment variable: The key variable of interest is the enrollment in the ACO by children with disabilities. This “treatment” was assigned to children seen by one of the health care facilities within PFK’s 34-county service area in Ohio beginning in July 2013. Data from PFK-enrolled children prior to enrollment (July 2010 – June 2013) will serve as primary controls, adjusting for age and length of time on Medicaid. Children who were enrolled in Ohio Medicaid with ABD eligibility in other areas of the state will serve as additional potential controls using Medicaid claims data. We cannot use these children as primary controls due to important limitations in the data, namely the inability to attribute children to other ACOs outside the 34 county PFK region. PFK’s unique arrangement with the state allows us to clearly identify the ACO catchment area by county and thus we can clearly attribute these patients to PFK.

Patient Characteristics: Our analysis is conducted on a diverse population of children and adolescents. Their characteristics vary by age, gender, race, Latino ethnicity, SSI status, county of residence, diagnoses, procedures received, length of time on Medicaid and other patient characteristics as detailed in **Appendix F**. We will create baseline disease adjustment categories using the Chronic Illness and Disability Payment System, which was specifically designed for disabled Medicaid enrollees. [48]

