The underlying population for this study is all children up to age 18 enrolled in the Partners for Kids (PFK) on May 30th 2015 who had been previously enrolled in fee-for-service (FFS) Medicaid and transitioned into PFK as a result of the ABD policy change. The primary analytic data comes from Ohio Medicaid administrative claims. Claims data have different missing data issues than do other primary or even secondary data sets on several dimensions. First, many of the fields are mandatory, which means fields such as procedure code and Medicaid eligibility status will

be 100% complete. Second, although claims data have the traditional limitations of any administrative data, including the lack of information of services paid fully out-of-pocket or financed through Medicare, only services provided through Medicaid will be used in the analysis, which will take a Medicaid/agency perspective. This means that services and expenditures will not aim to be a complete record, but those covered through the Medicaid program. We will clearly indicate the scope of analysis in publications. For the subsets of claims data merged with survey and medical records, we do not anticipate missing data problems for the same reasons above.

The estimated size of this population is 8,000. Because of the qualitative nature of Aim 1 we do not propose a missing data plan. The following assumptions have been made regarding rates of participation from this population for Aims 2 and 3:

Aim 2 – Caregiver Survey

We expect 34% percent of the eligible caregivers to complete the caregiver survey. This is based on assumptions from previous studies with this population regarding degree of incorrect addresses for the opt-out mailing, opt outs, missing/non-functional telephone numbers, and refusal when contacted.

- *Prevention of missingness*– We will use alternative sources of contact information (e.g. EHR records, internet look-up sites) for those families with missing telephone numbers.
- *Monitoring of missingness* – we will record and report the following statistics: % of invitation letters returned by the post office, % opting out, % bad telephone numbers that cannot be found after research, and % refusal by reached families. For each of these percentages, we will describe the lost respondents by gender, age, urban/rural residence, and diagnosis category using PFK data (note: race is not reliably available on the PFK data).

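### The dated survey items cover ACO months 13 to 28 at the earliest, not the first year after transition; the last-stay items are also a poor index for the 30-day readmission example

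*Combined protocol and SAP*

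**What the plan says.** On the period measured, the Aim 2 introduction says: "This tool will measure experiences with and documentation of care coordination in the first year after the transition to the ACO". The first of the three conclusions listed at the end of the Aim 2 Analysis section concerns "the quality and completeness of care coordination offered to ABD children upon roll-in to the ACO".

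On dates:
- Study Design, General Approach: "After the policy change went into effect in July 2013, all ABD children were required to enroll in managed care". The Aim 3 paragraph on the key treatment variable agrees, describing assignment within the "service area in Ohio beginning in July 2013".
- Handling Missing Data: the population is children "enrolled in the Partners for Kids (PFK) on May 30th 2015 who had been previously enrolled in fee-for-service (FFS) Medicaid".
- Procedures, Aim 2, Timeframe: the 1 July entry is "Begin web survey. CSRL send follow-up letters to eligible sample with code and web address" and the 31 October entry is "End date for telephone survey". No year is given.

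On recall, Attachment B specifies the survey (FECC) indicators. Most look back 12 months from the interview. Some look back 3 months, and the hospital items refer to the most recent overnight stay in the past 12 months.

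On linked analyses, the Aim 2 Analysis section gives as one example a test of "the relationship between receipt of a useful and understandable discharge summary following an inpatient stay and 30 day readmission".

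**The concern.** A recall survey measures the period before the interview. If interviews take place two years or more after the transition, a 12-month look-back describes the second ACO year or later. Reporting it as first-year performance would present an established programme as a start-up one. That matters here because Aim 2's first stated conclusion is about coordination at the point of entry, and because readers deciding whether an ACO can absorb this population will care about the early period.

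The second issue is one of time order. A discharge summary has to be tied to a particular stay before one can ask whether readmission followed within 30 days. The survey ties it to the last stay before interview, which is by definition a stay with no later admission up to the interview.

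**Working it through.** **Part 1: period covered**

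Inputs: transition July 2013 (General Approach; key treatment variable); population date 30 May 2015 (Handling Missing Data); fieldwork 1 July to 31 October (Timeframe); look-backs of 12 and 3 months (Attachment B).

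ACO month = 12 × (year − 2013) + calendar month − 6, so July 2013 is month 1. The stated first year is therefore months 1 to 12. The population date, 30 May 2015, is 12 × 2 + 5 − 6 = month 23.

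An interview on 1 July 2015 looks back over July 2014 to June 2015, months 13 to 24. One on 31 October 2015 looks back over November 2014 to October 2015, months 17 to 28. The same steps for other years give:

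| Survey year | 12-month items, first interviews | 12-month items, last interviews | 3-month items, all interviews |
|---|---|---|---|
| 2014 | 1–12 | 5–16 | 10–16 |
| 2015 | 13–24 | 17–28 | 22–28 |
| 2016 | 25–36 | 29–40 | 34–40 |

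Only a 2014 survey comes close to the stated period, and it cannot be reconciled with a population defined in May 2015.

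Indicator count in Attachment B:
- Period shown in the item or its screener: CC2, CC3, CC5, CC7, CC8, CC8c, CC9, CC10 (8); IE2 to IE6 (5); MH3a, MH3b, MH6 (3). Total 16.
- No period shown: MH8, SCP2, SCP4, SCP6. Total 4.

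Later entry: a child entering k months after July 2013 has a first year of months k + 1 to k + 12. Overlap with the 2015 windows (first interviews, then last interviews):
- July 2013 (k = 0): 0 and 0 months.
- October 2013 (k = 3, months 4–15): 3 and 0 months.
- January 2014 (k = 6, months 7–18): 6 and 2 months.

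The documents state no phase-in, so the last two rows are assumptions.

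**Part 2: readmission example, if the survey-reported last stay is the index**

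Suppose that stay ended d days before interview.
- If d is more than 30, the whole 30-day window lies before the interview. An overnight readmission inside it would itself have been the last stay. The count is zero by construction.
- If d is 30 or less, the first d days are already known to be free of readmission. Only 30 − d days remain to be seen in claims.

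For scale only, since the documents give no admission rate: with reported stays spread evenly over the year, 30/365 = 8.2% have any open window. With stays following a Poisson process at r per year, the share is (1 − exp(−30r/365)) / (1 − exp(−r)), which is 8.6% at r = 0.1 and 12.5% at r = 1.0. If rates vary strongly between children (gamma-Poisson, mean m = 1.0, shape k = 0.25), it is (1 − (1 + 30m/(365k))^−k) / (1 − (1 + m/k)^−k) = 20.7%. On these assumptions about 79% to 91% of reported stays are zero by construction. Length of stay is ignored.

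Two features of Attachment B add to this. IE5 and IE6 are scored only when a summary was received (item Q22 = yes). The only scored usefulness item (IE3c, item Q20) concerns main-provider visit summaries, not hospital summaries.

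**The case against.** On the period, the roll-in wording may simply name the population that was moved rather than a measurement date, and Attachment B already shows the recall windows to a careful reader. Both points are fair. Neither rescues the sentence in the Aim 2 introduction, which states a measurement period. Sample size, indicator scoring and estimators are unaffected, so this is a labelling error and not a flaw in the data collection.

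On readmission, the objection is stronger. The plan offers the test only as an example and fixes neither the source of the exposure nor the index stay. It counts 31 measures from the survey and the record review together. Attachment B holds 20, so about 11 are not in the available text, and a record-based discharge measure may be among them. A child-level outcome, such as any 30-day readmission in claims, would not be zero by construction, although the summary might then post-date the readmission. The raw item Q22 does separate children who received a summary from those who did not, and IE6 separates easy from not easy to understand among recipients. All of this stands, and it is why the second part is conditional.

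**Conclusion.** The first part holds: as written, the first-year period is wrong for the 16 dated survey indicators. They cover ACO months 13 to 28 at the earliest (months 22 to 28 for the 3-month items), and months 25 to 40 if the survey was in 2016. This rests on July 2013 entry and on 2015 as the earliest survey year, inferred from the population date.

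A reader might infer that no Aim 2 data can speak to the first year. The documents do not support that. The four undated indicators may reflect it, though they cannot isolate it. Children who entered later could overlap in part. The record-review look-back is not given in the available text.

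The second part is secondary and conditional. With the survey-reported last stay as index, the test would carry very little information and be biased toward finding no readmissions. A reader might go further and say that the survey items cannot be used at all or that no association could ever appear. That goes too far: a small window after interview remains, item Q22 gives a contrast, and the plan does not commit to this index. The percentages above are illustrations under assumed rates and do not carry the conclusion.

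The Aim 3 interrupted time series on claims is not touched by either part.

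**What to change.** **Period.** Reconcile the Aim 2 introduction, the Aim 2 Analysis section, Handling Missing Data and the Timeframe. State the survey year. Report survey results as the 12 months, the 3 months or the last stay before interview, and flag MH8, SCP2, SCP4 and SCP6 as having no stated period. Drop the first-year and roll-in wording as the period for survey measures, and state the record-review look-back. The cost is wording only.

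**Readmission example.** Do not use the survey-reported last stay as the index for 30-day readmission. There are two alternatives:
- Take the exposure and the index stay from the medical record or claims, if the abstraction tool captures discharge documentation. This is limited to families who consent to record review (1,000 expected) and have a stay in the reviewed records. It would show that a summary was given, not that it was understood.
- Among children with a stay in the past 12 months (item Q21 = yes), relate raw Q22 (yes or no) to admissions after interview, adjusted for earlier utilisation. This answers a somewhat different question.

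Both mean fewer events. In the second, follow-up is limited by claims ending in 2016. For a 2015 survey it is 8 to 12 months if claims stop in June 2016, and 14 to 18 months if they stop in December 2016. For a 2016 survey it is at most 6 months, which is hardly workable.
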